✓Compare

Institutional Review Board for Baylor College of Medicine and Affiliated Hospitals

Protocol Number: H-45486

Status: Closed

Initial Submit Date: 4/2/2019

Section Aa: Title & PI

A1. Main Title

EFFECT OF OPIOIDS ON VENTILATION IN CHILDREN WITH OBSTRUCTIVE SLEEP APNEA

A2. Principal Investigator

Name: [name]

[contact]

Id: 195273

Fax:

Department: ANESTHESIOLOGY: BCM

Email: [contact]

Center:

Mail Stn: BCM320

A3. Administrative Contact

Name: [name]

[contact]

Id: 160158

Fax:

Department: ANESTHESIOLOGY: BCM

Email: [contact]

Center:

Mail Stn: BCM320

Section Ab: General Information

A4. Co-Investigators

Name: [name]

[contact]

Id: 195204

Fax:

Department: ANESTHESIOLOGY: BCM

Email: [contact]

Center:

Mail Stn: BCM320

A5. Funding Source:

Baylor College of Medicine (Internal Funding Only)

A6a. Institution(s) where work will be performed:

TCH: Texas Children's Hospital

A6b. Research conducted outside of the United States:

Country:

Facility/Institution:

Contact/Investigator:

Phone Number:

If documentation of assurances has not been sent to the Office of Research, please explain:

A7. Research Category:

A8. Therapeutic Intent

Does this trial have therapeutic intent?

Not set yet

A9. ClinicalTrials.gov Registration

Section B: Exempt Request

B. Exempt From IRB Review

Not Applicable

Section C: Background Information

Ventilatory suppression in children following opioid administration is of obvious concern, especially following routine surgical procedures (i.e. adenotonsillectomy). It is thought that patients with obstructive sleep apnea (OSA) have increased sensitivity to opioids, especially in opioid naïve patients. Recent evidence in adults suggests that patients with moderate to severe OSA may not predispose patients to increased opioid sensitivity in the form of respiratory depression when compared with patients that do not have OSA. It is well known that OSA in children is significantly different from OSA in adults (e.g. gender predilection, central vs. peripheral causation). The manifestation and etiologies are very different in pediatric OSA making it a vastly different disease process. The aim of this study is to identify if children with known OSA experience opioid induced respiratory depression with greater incidence then in children without OSA.

Section D: Purpose and Objectives

The sole objective in this study is to evaluate if routine amounts of opioids given for tonsillectomy in children have greater amounts of respiratory depression in children with documented obstructive sleep apnea when compared with patients that do not have obstructive sleep apnea

Section E: Protocol Risks/Subjects

E1. Risk Category

Category 3: Research involving greater than minimal risk and no prospect of direct benefit to the individual subject, but likely to yield generalizable knowledge about the subject's disorder or condition.

E2. Subjects

Gender:

Both

Age:

Child (3-12 yrs), Infant/Toddler (0-36 mos)

Ethnicity:

All Ethnicities

Primary Language:

English, Spanish

Groups to be recruited will include:

Asymptomatic patients with chronic conditions, healthy; Patients

Which if any of the following vulnerable populations will be recruited as subjects?

Children

Vulnerable populations require special protections. How will you obtain informed consent, protect subject confidentiality, and prevent undue coercion?

Parents will be approached as ask to participate in the study. They will be informed that this is completely voluntary and that they can choose to avoid participation and/or revoke their participation at any point. Their participation or lack thereof will not change or alter the care their child will receive. The risks include loss to confidentiality and we will reduce this risk by only having the PI and co-investigators collect data which will be stored only on the BCM firewall. Additionally, there is a risk of apnea with all opioids however this risk is routinely managed by pediatric anesthesiologists and encountered in nearly all anesthetics.

E3. Pregnant woman/fetus

Will pregnant women and/or fetuses (as described in 45 CFR 46 Subpart B) be enrolled in the research?

No

E4. Neonates

Will neonates of uncertain viability or nonviable neonates (as described in 45 CFR 46 Subpart B) be enrolled in the research?

No

E5. Children

Will children be enrolled in the research?

Yes

Section F: Design/Procedure

F1. Design

Select one category that most adequately describes your research:

c) Pilot

Discuss the research design including but not limited to such issues as: probability of group assignment, potential for subject to be randomized to placebo group, use of control subjects, etc.

The Principal and/or co-investigators will identify children meeting enrollment criteria from the daily operative list at Texas Children's Hospital main campus. Those meeting enrollment criteria will be approached by the PI and/or co-investigators.

The study is a prospective randomized trial to identify the effect of opioids on children with obstructive sleep apnea

F2. Procedure

Patient Identification The Principal and/or co-investigators will identify children meeting enrollment criteria from the daily operative list at Texas Children's Hospital main campus. Those meeting enrollment criteria will be approached by the PI and/or co-investigators.

Control Group: Patients undergoing tonsillectomy/adenotonsillectomy without tonsillectomy Children presenting for tonsillectomy/adenotonsillectomy for recurrent infection. Children with negative sleep studies will be included. Those without formal sleep studies will be screened using the OSA 18 questionnaire, a validated clinical assessment score for pediatric sleep-disordered breathing.

Those with negative questionnaire scores will be included.

Study Group: Patients with Moderate to Severe OSA as documented by formal polysomnography For the study group, patients will be included if they have undergone formal sleep study evaluations. Stratification will be based on the polysomnography testing using the apnea hypopnea index (AHI) and/or the number desaturation events according to the McGill Scoring system for pediatric OSA. Patients with AHI greater than 6 will be considered to have moderate to severe OSA and thus eligible for inclusion

All patients will undergo general anesthesia per the usual practice at Texas Childrens Hospital according to the preferences of the anesthesiology attending physician. Induction will be sevoflurane/+nitrous oxide followed by intravenous access secured.

Endotracheal intubation using a RAE endotracheal tube will be performed with the size selected using the formula: Predicted Size Cuffed Tube = (Age / 4) + 3. Following endotracheal intubation, spontaneous ventilation will be maintained without the use of continuous positive pressure. Sevoflurane will be reduced to maintain between 0.5-0.7 MAC according to the Drager Apollo anesthesia machine. The patient will be allowed to establish their respiratory equilibrium for 3 minutes following intubation on 0.21% oxygen. Baseline tidal volume (TV), respiratory rate (RR) and end-tidal carbon dioxide (ETCO2) will be recorded. fentanyl 1mcg/kg will be administered as a bolus (usual clinical practice). The TV, RR, ETCO2 will be recorded, at 5 and 10 minutes After opioid administration. Apnea or desaturation (<92%) will be treated by assisting ventilation as required (standard practice). After 10 minutes,(to a repeated dose effect) a second dose of 1mcg/kg will be administered with the same TV, RR, ETCO2 recorded for 5 minutes.

Surgery will commence as usual with additional medication to be administered at the discretion of the anesthesiology providers. No change to standard practice will occur the research portion will be prospectively recorded the TV, RR, ETCO2 following opioid administration to calculate change from baseline (pre-opioid), routine fentanyl administration for these procedures is 2 mcg/kg

Section G: Sample Size/Data Analysis

G1. Sample Size

How many subjects (or specimens, or charts) will be used in this study?

Local: 50 Worldwide: 50

Please indicate why you chose the sample size proposed:

Our sample size is based on a recent 2019 landmark paper investigating a similar question in adults with obstructive sleep apnea we propose to enroll 20 control patients and 30 patients with documented obstructive sleep apnea

G2. Data Analysis

Provide a description of your plan for data analysis. State the types of comparisons you plan (e.g. comparison of means, comparison of proportions, regressions, analysis of variance). Which is the PRIMARY comparison/analysis? How will the analyses proposed relate to the primary purposes of your study?

The primary outcome will be measurement of continuous variables of tidal volume, respiratory rate and end tidal CO2. these will be reported as means with SD, regression analysis will be performed for patients falling into the moderate and severe categories of obstructive sleep apnea by sleep study.

Section H: Potential Risks/Discomforts

H1. Potential Risks

Describe any potential risks/discomforts; (physical, psychological, social, legal, or other) and assess the likelihood and seriousness of such risks:

Confidentiality and we will reduce this risk by only having the PI and co-investigators collect data which will be stored only on the BCM firewall.

Asymptomatic patients with chronic conditions, healthy; Patients

Children

Parents will be approached as ask to participate in the study. They will be informed that this is completely voluntary and that they can choose to avoid participation and/or revoke their participation at any point. Their participation or lack thereof will not change or alter the care their child will receive. The risks include loss to confidentiality and we will reduce this risk by only having the PI and co-investigators collect data which will be stored only on the BCM firewall.

Those with negative questionnaire scores will be included.

Study Group: Patients with Moderate to Severe OSA as documented by formal polysomnography For the study group, patients will be included if they have undergone formal sleep study evaluations. Stratification will be based on the polysomnography testing using the apnea hypopnea index (AHI) and/or the number desaturation events according to the McGill Scoring system for pediatric OSA. Patients with AHI greater than 6 will be considered to have moderate to severe OSA and thus eligible for inclusion

All patients will undergo general anesthesia per the usual practice at Texas Childrens Hospital according to the preferences of the anesthesiology attending physician. Induction will be sevoflurane/+nitrous oxide followed by intravenous access secured.

Endotracheal intubation using a RAE endotracheal tube will be performed with the size selected using the formula: Predicted Size Cuffed Tube = (Age / 4) + 3. Following endotracheal intubation, spontaneous ventilation will be maintained without the use of continuous positive pressure. Sevoflurane will be reduced to maintain between 0.5-0.7 MAC according to the Drager Apollo anesthesia machine. The patient will be allowed to establish their respiratory equilibrium for 3 minutes following intubation on 0.21% oxygen. Baseline tidal volume (TV), respiratory rate (RR) and end-tidal carbon dioxide (ETCO2) will be recorded. fentanyl 1mcg/kg will be administered as a bolus (usual clinical practice). The TV, RR, ETCO2 will be recorded, at 5 and 10 minutes After opioid administration. Apnea or desaturation (<92%) will be treated by assisting ventilation as required (standard practice). After 10 minutes,(to a repeated dose effect) a second dose of 1mcg/kg will be administered with the same TV, RR, ETCO2 recorded for 5 minutes.

H2. Discomforts

Describe any potential discomforts; (physical, psychological, social, legal, or other) and assess the likelihood and seriousness of such discomforts:

Confidentiality and we will reduce this risk by only having the PI and co-investigators collect data which will be stored only on the BCM firewall.

Asymptomatic patients with chronic conditions, healthy; Patients

Children

Parents will be approached as ask to participate in the study. They will be informed that this is completely voluntary and that they can choose to avoid participation and/or revoke their participation at any point. Their participation or lack thereof will not change or alter the care their child will receive. The risks include loss to confidentiality and we will reduce this risk by only having the PI and co-investigators collect data which will be stored only on the BCM firewall.

Those with negative questionnaire scores will be included.

Study Group: Patients with Moderate to Severe OSA as documented by formal polysomnography For the study group, patients will be included if they have undergone formal sleep study evaluations. Stratification will be based on the polysomnography testing using the apnea hypopnea index (AHI) and/or the number desaturation events according to the McGill Scoring system for pediatric OSA. Patients with AHI greater than 6 will be considered to have moderate to severe OSA and thus eligible for inclusion

All patients will undergo general anesthesia per the usual practice at Texas Childrens Hospital according to the preferences of the anesthesiology attending physician. Induction will be sevoflurane/+nitrous oxide followed by intravenous access secured.

Endotracheal intubation using a RAE endotracheal tube will be performed with the size selected using the formula: Predicted Size Cuffed Tube = (Age / 4) + 3. Following endotracheal intubation, spontaneous ventilation will be maintained without the use of continuous positive pressure. Sevoflurane will be reduced to maintain between 0.5-0.7 MAC according to the Drager Apollo anesthesia machine. The patient will be allowed to establish their respiratory equilibrium for 3 minutes following intubation on 0.21% oxygen. Baseline tidal volume (TV), respiratory rate (RR) and end-tidal carbon dioxide (ETCO2) will be recorded. fentanyl 1mcg/kg will be administered as a bolus (usual clinical practice). The TV, RR, ETCO2 will be recorded, at 5 and 10 minutes After opioid administration. Apnea or desaturation (<92%) will be treated by assisting ventilation as required (standard practice). After 10 minutes,(to a repeated dose effect) a second dose of 1mcg/kg will be administered with the same TV, RR, ETCO2 recorded for 5 minutes.

H3. Confidentiality

Will this research require a waiver of informed consent?

NA

H4. Waiver of informed consent

Will this research require a waiver of informed consent?

NA

H5. Consent

Will this research require a waiver of informed consent?

NA

H6. Documentation of informed consent

Will this research require a waiver of informed

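### Section F1 calls the study randomised, but diagnosis sets the groups, and G2 plans no adjusted OSA-control comparison to stand in for randomisation

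*Combined protocol and SAP*

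**What the plan says.** - **Design label (F1, selected category Pilot).** "The study is a prospective randomized trial to identify the effect of opioids on children with obstructive sleep apnea".
- **Objective (Section D).** The one objective is whether routine opioid amounts produce "greater amounts of respiratory depression in children with documented obstructive sleep apnea when compared with patients that do not have obstructive sleep apnea".
- **How groups are formed (F2).** Controls are "Children presenting for tonsillectomy/adenotonsillectomy for recurrent infection", with a negative sleep study or, where there is none, a negative OSA 18 score. For the study group: "Patients with AHI greater than 6 will be considered to have moderate to severe OSA and thus eligible for inclusion".
- **What is given (F2).** One sequence is described, with no distinction by group. After baseline readings, "fentanyl 1mcg/kg will be administered as a bolus (usual clinical practice"), with readings at 5 and 10 minutes, then a second dose of the same size and further readings.
- **What is computed (F2).** The research element is recording "TV, RR, ETCO2 following opioid administration to calculate change from baseline (pre-opioid").
- **Analysis (G2).** Tidal volume (TV), respiratory rate (RR) and end-tidal CO2 (ETCO2) are together the primary outcome, summarised as means with SD. In addition, "regression analysis will be performed for patients falling into the moderate and severe categories of obstructive sleep apnea by sleep study".
- **Size and ages.** G1 plans 20 controls and 30 children with OSA. The age categories ticked in E2 run from infancy to 12 years.

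**The concern.** Randomisation would balance the groups on average for age, size and everything else, and so allow a simple comparison of means to be read causally. Here that property is claimed but absent, and G2 puts nothing in its place.

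Three things could then separate the groups apart from OSA:

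- **Body size.** Absolute TV scales with size. Taking change from baseline reduces differences in starting level, but a change in mL still scales with the child. The documents do not say whether TV is in mL or per kg, or whether the change is absolute or percentage.
- **Age.** The age span is wide. Confounding of RR and ETCO2 by age is plausible, though the documents do not show it.
- **Surgical indication.** Controls are chosen for recurrent infection and no indication is stated for the OSA group, so indication may be inseparable from OSA status.

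A reader who trusts the F1 label could take a difference due partly to age or size as an effect of OSA on opioid sensitivity.

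**Working it through.** **1. Is anything randomised?** Setting the sections side by side:

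| Feature of a randomised trial | What the protocol has |
|---|---|
| Assignment by chance | Assignment by diagnosis (F2) |
| Two or more treatments to assign | One fentanyl sequence for all (F2) |
| Sequence, ratio by chance, concealment | None described; 20 and 30 are recruitment targets (G1) |
| Stratified allocation | F2's stratification refers to sleep-study severity, not allocation |

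OSA status cannot be assigned, and there is no second treatment to assign. The label is wrong as written.

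**2. Does G2 address the objective?** The objective contrasts OSA with no OSA. G2's summaries are descriptive, and its regression concerns the moderate and severe OSA categories. No OSA-control test or model is named, adjusted or not, and no covariate is listed.

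**3. The plan's own figure.** 20 + 30 = 50 agrees with the stated total. The basis for 50 cannot be reproduced: G1 cites an adult study and gives no effect size, SD, alpha or power.

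**4. Body size, with assumed weights.** Suppose TV falls by the same x mL/kg in both groups, unrelated to weight. The mean fall in mL is then x times mean weight, so the ratio of mean falls equals the ratio of mean weights. With assumed mean weights of 25 and 20 kg, 25/20 = 1.25. That is a 25% difference in mL with no OSA effect. For example, a 30% fall from an assumed 7 mL/kg is 0.3 × 7 × 25 = 52.5 mL against 0.3 × 7 × 20 = 42 mL. On a per-kg scale both are 2.1 mL/kg.

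**5. False positives under bias, with assumed inputs.** The plan names no test, so I assume a two-sided t-test at 5%.

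- From G1: n = 20 and 30, so df = 48 and SE = √(1/20 + 1/30) = 0.289 SD.
- Bias in outcome SDs = age imbalance (SD) × age-outcome correlation, both assumed.
- The rejection rate with no true OSA effect comes from the noncentral t with noncentrality bias/0.289.

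| Age imbalance × correlation | Bias (SD) | False-positive rate |
|---|---|---|
| 0.25 × 0.2 | 0.05 | 5.3% |
| 0.25 × 0.5 | 0.125 | 7.1% |
| 0.5 × 0.5 | 0.25 | 13.6% |
| 1.0 × 0.3 | 0.3 | 17.5% |
| 1.0 × 0.5 | 0.5 | 39.7% |

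A separate normal-approximation calculation agrees where the two overlap: 7.2% at 0.125 SD and 13.9% at 0.25 SD.

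**The case against.** The strongest reply accepts the facts and disputes their weight.

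- **It is a pilot.** F1 selects that category, which lowers what can be asked of 50 children in formal power and modelling. It does not make groups set by diagnosis randomised, nor does it supply the missing comparison.
- **The label misleads nobody, since F2 defines the groups straight afterwards.** There is something in this: the word alone is an editorial repair. The substantive gap is in G2, which contains nothing to prevent a causal, unadjusted reading.
- **The mL example assumes an unfavourable scale.** This stands as a limit. If the change were a percentage, the same per-kg fall from the same per-kg baseline would give equal values at 20 and 25 kg. But the plan fixes no scale, and stating TV per kg settles the matter.
- **The error rates rest on assumed inputs and on a test the plan does not name.** Also true. They show how sensitive a comparison of this size is to imbalance; they do not estimate the bias in this study. The 40% figure needs a full 1 SD age imbalance.
- **The model leaves open three outcomes and several time points.** Correct, but choosing among them and controlling multiplicity is a separate matter.
- **Indication and OSA status are entangled by the choice of controls.** Yes, so it belongs among the limitations, not the covariates.

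**Conclusion.** The concern holds. The randomised label in F1 is contradicted by F2, and no other section cures it. Followed as written, G2 gives no confounder-controlled answer to the study's only objective; it does not name even an unadjusted OSA-control comparison. These conclusions rest on the text alone.

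The numerical consequence cannot be fixed from the documents. The range of about 5% to 40% false positives depends on the assumed test, alpha, age imbalances and correlations. The 25% difference in TV fall depends on the assumed weights and on change being analysed in mL. Whatever its size, the OSA-control result can support an association only. This should be corrected.

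**What to change.** 1. **F1:** replace the randomised description with *prospective non-randomised cohort comparison of children with and without OSA*.
2. **G2:** state the primary OSA-control comparison as a regression of each post-opioid outcome on group, adjusted for the pre-opioid value and age. Express TV per kg (or add weight as a covariate), and show the unadjusted difference beside the adjusted one.
3. **Reporting:** word the OSA-control conclusion as an association. State as a limitation that controls are selected for recurrent infection, so indication may not be separable from OSA status.

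**Cost.** No new measurement is needed. Age already enters the tube formula ("Predicted Size Cuffed Tube = (Age / 4) + 3") and weight is needed for the per-kg dose. F2 lists only TV, RR and ETCO2 as recorded, so a line should say that age and weight are kept for analysis. Baseline and age use two degrees of freedom, taking the residual from 48 to 46. Using both age and weight as covariates would bring some collinearity, which TV per kg avoids. The protocol's status is shown as closed, so if the adjusted model is added only now, it should be reported as not prespecified.

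### Drugs and anaesthetic depth that F2 leaves open before baseline are neither recorded for analysis nor adjusted for, so in groups defined by OSA status they could hide or mimic an OSA effect.

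*Combined protocol and SAP*

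**What the plan says.** **Fixed for both groups (F2).** "Induction will be sevoflurane/+nitrous oxide followed by intravenous access secured". After intubation, with spontaneous ventilation, "Sevoflurane will be reduced to maintain between 0.5-0.7 MAC according to the Drager Apollo anesthesia machine". Then "The patient will be allowed to establish their respiratory equilibrium for 3 minutes following intubation". After that "Baseline tidal volume (TV), respiratory rate (RR) and end-tidal carbon dioxide (ETCO2) will be recorded", and "fentanyl 1mcg/kg will be administered as a bolus (usual clinical practice"). A second equal bolus follows at 10 minutes.

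**Left open (F2).** The anaesthetic as a whole is given "according to the preferences of the anesthesiology attending physician". No rule says when nitrous oxide is added or where within the MAC range a child should sit. Premedication and intravenous drugs given around intubation are not mentioned. A later sentence reads "Surgery will commence as usual with additional medication to be administered at the discretion of the anesthesiology providers", but it concerns the surgery, after the study readings.

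**Group formation (F1, F2).** F1 calls the study randomised. F2 forms the groups by diagnosis: moderate to severe OSA on polysomnography, against children operated on for recurrent infection with a negative sleep study or questionnaire.

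**Recording and analysis (F2, G2).** Tidal volume, respiratory rate and end-tidal CO2 are the only variables named for recording, and F2 uses them as change from the pre-opioid baseline. G2 plans means with SD and a regression on the moderate and severe OSA categories. It names no covariate for anaesthetic drugs or depth.

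**The concern.** The sole objective (Section D) is to compare opioid-induced respiratory depression between children with and without OSA. Other ventilatory depressants given before baseline act on the same three outcomes. Section C reports the belief that OSA patients are more sensitive to opioids. A clinician who shares it has a reason to give these children fewer such drugs, or to keep them lighter. That would be confounding by indication, and with groups defined by disease nothing in the design balances it.

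The bias could run either way. If controls receive more depressant and respond more to fentanyl because of it, a true OSA effect is hidden. The opposite pattern would create a false one. With neither the exposures nor an adjustment in the plan, a reader of the results could not tell which had happened.

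**Working it through.** **1. The plan's own figure.** G1 gives 20 controls and 30 OSA children, 50 in all, with no alpha, sidedness, power, effect size or SD. The 50 therefore cannot be reproduced. What it can detect has to be worked back under assumed conventions.

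**2. Detectable difference (assumed two-sided 5%, 80% power).** The SE of a difference in means, in SD units, is sqrt(1/20 + 1/30) = 0.289. By normal approximation the detectable difference is (1.96 + 0.84) × 0.289 = 0.81 SD. By t-test on 48 degrees of freedom it is 0.825 SD.

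**3. What change from baseline removes.** Suppose a drug lowers a child's ventilation by the same amount at baseline and at every later reading. Its effect cancels in the subtraction. Two things do not cancel: a drug that changes the size of the fentanyl response, and a drug whose effect fades during the readings. The readings span about 10 + 5 = 15 minutes, and baseline comes 3 minutes after intubation, so a drug given for intubation could still be wearing off.

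**4. Size, on assumed inputs only.** Bias in SD units = (difference between groups in the share exposed) × (shift in the change score caused by exposure). The documents supply neither input. The last two columns use the t-test. The final one takes a true effect of 0.825 SD and a bias that opposes it.

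| Exposure gap | Shift in change score | Bias | Rejection rate with no OSA effect | Power |
|---|---|---|---|---|
| 20 points | 0.25 SD | 0.05 SD | 5.3% | 75% |
| 40 points | 0.25 SD | 0.10 SD | 6.3% | 69% |
| 20 points | 0.5 SD | 0.10 SD | 6.3% | 69% |
| 40 points | 0.5 SD | 0.20 SD | 10.4% | 56% |
| 20 points | 1.0 SD | 0.20 SD | 10.4% | 56% |
| 40 points | 1.0 SD | 0.40 SD | 27% | 30% |

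The largest entry is 0.40/0.825 = 48% of the detectable difference.

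**5. Price of adjusting.** A comparison with intercept, group and baseline leaves 50 - 3 = 47 error degrees of freedom, and one exposure term leaves 46. Overlap between exposure and group also costs precision. Take 60% of controls (12 of 20) and 20% of OSA children (6 of 30) exposed, a 40-point gap. The overall share exposed is 18/50 = 0.36. The squared correlation between group and exposure is (0.6 × 0.4 × 0.4)² / (0.6 × 0.4 × 0.36 × 0.64) = 0.167. The SE grows by 1/sqrt(1 - 0.167) = 1.095, about 10%, before any gain from variance explained.

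**6. Price of excluding exposed children.** In the same example 8 controls and 24 OSA children remain. The detectable difference by normal approximation is 2.80 × sqrt(1/8 + 1/24) = 1.14 SD, against 0.81 SD for the full sample.

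**The case against.** The strongest reply is that F2 is already largely standardised. Induction, ventilation mode, MAC range, equilibration and opioid dose are the same in both groups, the expressly discretionary medication comes after the readings, and the outcome is a change score. Premedication and intravenous adjuncts are nowhere mentioned, so their use is inferred from silence. The study is labelled a pilot, and every bias figure is assumed.

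Much of this stands. A reader might infer that the whole anaesthetic up to baseline is at the attending's choice; F2's fixed elements contradict that. A reader might also infer that OSA status cannot be kept from the attending. The documents say only that groups rest on diagnosis and describe no blinding, so the attending can know it, and no more is established. Finally, a reader might infer that investigators who know the group choose readings off a monitor. The phrase "only having the PI and co-investigators collect data" belongs to a confidentiality statement in E2, and no section says how the readings are captured. Recorder bias is therefore not part of this point.

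The reply does not close the gap. The sentence on the attending's preference covers the period before baseline, and nitrous oxide and the position within the MAC range are open on the face of F2. The change score cancels only a constant shift. A pilot that compares groups is still exposed to confounding, which does not shrink with sample size.

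**Conclusion.** The concern holds in a limited form. As written, the plan cannot separate an OSA effect from a difference between non-randomised groups in pre-baseline depressants or anaesthetic depth, because it neither records these for analysis nor adjusts for them.

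The documents do not show that such a difference exists, and they fix neither its direction nor its size. The range of 0.10-0.40 SD rests on an assumed 20-40 point exposure gap and an assumed 0.5-1.0 SD shift in the change score, not in the level. With a 0.25 SD shift the bias is at most 0.10 SD and does little harm. The 0.83 SD benchmark itself assumes two-sided 5% and 80% power. This is something the plan should put right cheaply, not a flaw that by itself defeats the study.

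**What to change.** **Record.** From the anaesthesia record, copy every sedative, opioid and other anaesthetic drug (drug, amount, time) given before baseline and up to the last study reading. Add nitrous oxide use and the MAC value at each reading. Report all of these by group.

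**Analyse.** Add to G2 a comparison of the groups on each outcome, with the baseline value and pre-baseline sedative/opioid exposure (yes/no) as covariates. Show the unadjusted comparison beside it. Present any analysis that leaves out exposed children as descriptive only, because few controls may remain.

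**Cost.** A few extra data fields, one error degree of freedom and some loss of precision if exposure and group overlap strongly. G2 states no baseline-adjusted group comparison, so that model has to be written down as well. A yes/no covariate adjusts only partly, since it ignores amount and timing; the by-group table lets readers judge what remains. No extra staff and no change to anaesthetic care are proposed. The protocol's status is given as closed; if the anaesthesia records were kept, the exposures could still be extracted, with the adjusted analysis labelled as added later.
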